from organizational leaders, providers, and patients to better understand the facilitators and barriers to implementation and to guide refinements of the CDS.

Group-Randomized Study Eligibility Criteria

Study Sites: The group-randomized controlled study will be implemented in 34 Essentia Health primary care clinics in Minnesota, North Dakota, and Wisconsin. Essentia clinics have used the Epic® EHR since 2004 and have, on average, 14 PCPs (range: 1-56) and 377 prediabetes patients at high CV risk per clinic. Eighty-four percent of the Essentia geographic service area is rural, with 56% of the patient population and 66% of clinics located in this rural area. Average household incomes are less than \$35,000 for 42% of patients, and 45% live in health professional shortage areas.

Study Participants: PCPs and Patients: To participate, PCPs must practice at one of the 34 Essentiaclinics and meet these eligibility criteria: (a) be an adult-care general internist, family physician, non-obstetric nurse practitioner, or physician assistant, and (b) provide ongoing primary care for 15 or more prediabetes adults ages 18-75 with high CV risk. There are currently 441 eligible PCPs which should ensure a more robust understanding of implementation barriers and facilitators in a large PCP community.

To be considered for inclusion in primary or secondary analyses, **patients** must meet all the following eligibility criteria at the time of their indexvisit: (a) be 18-75 years old, (b) have no evidence of diabetes in the previous 12 months (based on lab values, diagnosis codes, use of medications, or on problem list), (c) not be pregnant (d) have the most recent fasting plasma glucose of 100-125 mg/dL or HbA1c 5.7-6.4% within the prior 24 months, (e) have the most recent BMI $\geq 25 \text{ kg/m}^2$, (f) have at least one of the following uncontrolled CV risk factors: current smoking, a diagnosis

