Aim #1- (a) Cardiovascular Risk Trajectories (H1): There is no validated CV risk engine developed with a prediabetes population. Therefore, we propose to use the ACC/AHA 10-year pooled CV risk engine to estimate annual rate of change in CV risk as our primary outcome. We will use the lipid equation for patients with lipid data available to calculate CV risk at the index and all post-index visits and, to minimize missing CV risk values, the BMI equation at the index and all post-index visits for the remaining patients. The BMI equation estimates higher CV risk relative to the lipid equation. Because the calculation method will be consistent across all visits within each patient this difference will not bias the estimated rate of change in CV risk. CV risk scores for each patient will be calculated at each primary care visit from the index through the entire follow-up period using available EHR data elements. As depicted in Figure 2 Step A, at each visit we will search for the most recent data elements, looking back over a period appropriate for each risk component (i.e., 12 months for BP values or medications, DM diagnosis, smoking, BMI; 48 months for lipids). H1 will be supported if the annual rate of change in CV risk scores from the index visit through the end of the follow-up period is lower (ie, less increase) among patients in the CDS relative to UC clinics; (b) Modifiable diabetes and CV risk factors (H2): Risk factors needed to calculate the CV risk scores (weight, systolic blood pressure, HDL-c, LDL-c, totalcholesterol, smoking), are extracted from EHR files as in Figure 2 Step A. H2 will be supported if annual rate of change in CV risk component trajectories are lower among patients in the CDS relative to UC clinics; (c) Metformin and statin use (H3): Data to assess drug treatment are from EHR files such as prescribed medications. The presence or absence of appropriate drug use will be assessed at each visit. H3 will be supported if appropriate drug use improves over the follow-up period among patients in the CDS clinics relative to UC patients.

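### Diabetes is screened over 12 months but the prediabetes lab may be 24 months old, and the risk score also looks back only 12 months for a diabetes diagnosis

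*Combined protocol and SAP*

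**What the plan says.** The combined protocol and SAP sets patient eligibility under Group-Randomized Study Eligibility Criteria, Study Participants. Patients "must meet all the following eligibility criteria at the time of their indexvisit", so the criteria apply jointly. Two of them concern glycaemic status:

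- Criterion (b): "have no evidence of diabetes in the previous 12 months (based on lab values, diagnosis codes, use of medications, or on problem list".
- Criterion (d): "have the most recent fasting plasma glucose of 100-125 mg/dL or HbA1c 5.7-6.4% within the prior 24 months".

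The text does not explain why the windows differ. It does not say whether 'most recent' applies to each test separately or to the later of the two, or what happens when glucose and HbA1c disagree.

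Under Definition and Measurement of Variables, Aim #1 (a), the CV risk score is computed at every primary care visit from the most recent data within a stated look-back for each component: "12 months for BP values or medications, DM diagnosis, smoking, BMI; 48 months for lipids". The eligibility section gives 26 to 38 months of follow-up. The primary outcome is the annual rate of change in this score.

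**The concern.** Hypotheses 1 to 4 are about patients with prediabetes. Criterion (b) counts lab values and diagnosis codes as evidence of diabetes, but evidence older than 12 months is ignored while a prediabetes-range lab of the same age still qualifies the patient. Some patients with evidence of diabetes by the plan's own standard can therefore be analysed as prediabetes.

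The second issue affects the outcome itself. Diabetes diagnosis is a listed component of the primary score, and its memory is shorter than the follow-up. If an empty window is scored as no diabetes, a recorded diagnosis can switch off. The patient's trajectory then shows a fall in risk that comes from record-keeping. Conversely, a patient admitted with older diabetes evidence can start with the component off and show an artificial rise when the diagnosis is next coded. Both disturb the slope that Hypothesis 1 tests.

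**Working it through.** This is a point of eligibility logic, so the plan has no figure to reproduce. The inputs are the windows in (b), (d) and the Aim #1 look-back list. 'Above range' means above the upper limits in (d); the plan states no separate lab cut-off for (b).

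**1. Lab patterns.** Take two labs, each fasting glucose or HbA1c, at two different times among 3, 9, 15 and 21 months before index, with no code, drug or problem-list entry for diabetes. There are 6 pairs of times × 4 pairs of tests = 24 patterns for each order of results.

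*Older lab in range, newer lab above range (24 patterns).*
- Newer lab at 3 or 9 months: 5 time pairs × 4 = 20, all excluded by (b).
- Newer lab at 15 months, older at 21: 1 × 4 = 4. Of these, 2 use the same test and are excluded by 'most recent' in (d).
- The other 2 use different tests. They are eligible if 'most recent' is read per test, and not eligible if it means the single latest result. Example: glucose 118 mg/dL at month -20, then HbA1c 7.0% at month -15.

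*Older lab above range, newer lab in range (24 patterns).*
- Older lab at 9 months: 1 × 4 = 4, excluded by (b).
- Older lab at 15 or 21 months: 5 × 4 = 20, eligible under both readings.

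| Rule | Newer lab above range: eligible | Older lab above range: eligible |
|---|---|---|
| As written, 'most recent' per test | 2 of 24 | 20 of 24 |
| As written, single latest result | 0 of 24 | 20 of 24 |
| Look-back in (b) set to 24 months, either reading | 0 of 24 | 0 of 24 |

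These are counts of logical patterns and say nothing about how many patients follow each one.

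**2. Diagnosis code.** Suppose a code is entered once at month -15, is not repeated and is not on the problem list, and the latest labs are in the prediabetes range. Criterion (b) does not see it and (d) is met, under both readings.

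**3. Lapse after index.** A diagnosis recorded once at month t is outside the look-back at visits after month t + 12. It can lapse before follow-up ends if t + 12 is less than the length of follow-up:
- shortest follow-up: t < 26 − 12 = 14 months;
- longest follow-up: t < 38 − 12 = 26 months.

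For example, a diagnosis recorded once at month 6 is out of the window after month 18. This rests on two assumptions: that an empty window is scored as no diabetes, and that the score is higher with diabetes than without.

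**The case against.** The strongest objection concerns the headline a reader might draw, that anyone with a newer diabetes-range lab can enter as prediabetes. The documents do not support this. A newer result above range on the same test fails (d) at any age, and one on either test within 12 months fails (b). Only a discordant result on the other test, 12 to 24 months old, gets through, and only under the per-test reading. That part of the objection stands in full. It does not touch the older-lab and single-code routes, which are open under both readings.

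The problem list, prescriptions and repeat coding narrow the eligibility gap. The lapse after index requires a diagnosed patient to go 12 months without diabetes being recorded again. The eligibility section reports a median of 6 primary care visits in 24 months, about 3 a year, so repeat coding is likely for many patients. The measurement section does not say how an empty window is scored or whether problem-list entries count. It refers to Appendix A for measuring variables, which is not in the text reviewed and may settle both questions. This limits the likely size but does not remove the stated 12-month rule.

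A reader might also infer that the decision support system manages these patients as prediabetes. That does not follow. Criteria (b) and (d) govern inclusion in the analyses, while the alert described in Step D states no diabetes look-back.

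Finally, a reader might infer bias between arms. The criteria are the same in both arms and the model adjusts for the index value. Step F does expect faster recognition of diabetes in intervention clinics, so recording after index could differ by arm, but the documents establish neither the size nor the direction of any effect.

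**Conclusion.** The point holds in a limited form. As written, (b) and (d) allow patients with evidence of diabetes 12 to 24 months before index into the prediabetes cohort by three routes, one of which depends on how 'most recent' is read. Separately, the 12-month look-back allows a diagnosis recorded once to leave the primary score within even the shortest follow-up, subject to the two scoring assumptions above.

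The number of patients affected is unknown. The documents give no frequency, and any percentage applied to the anticipated 6,600 patients would be a guess; that total also covers ages 18 to 75, whereas the Aim 1 analyses are restricted to 40 to 75. The effect is probably small. What is shown is an imprecise population definition and avoidable noise in the slope outcome. A biased treatment comparison is not shown. The lapse deserves more attention than the eligibility gap because it acts directly on the primary outcome.

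**What to change.** 1. In criterion (b), set the look-back for evidence of diabetes to 24 months, to match (d). In the check above this closes both lab sequences under either reading, and it also catches a code entered in months 12 to 24.
2. In criterion (d), state that the latest glycaemic result of either type must not be above the prediabetes range. Once (b) is changed this excludes no further pattern in the check; its value is to settle how discordant tests are handled. On its own it would leave the older-lab route open.
3. In the Aim #1 look-back rule, carry a diabetes diagnosis recorded after index forward to the end of follow-up.

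The Aim 1 data are collected retrospectively from the EHR, so these are changes to a cohort query and one input rule. The Specific Aims already report lack of efficacy, so results are known. If the main rules are not changed, the revised rules should at least be run as a labelled sensitivity analysis, with the number of patients who change status reported.

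The cost is a small loss of patients, some of whom may have prediabetes by their current labs, and an erroneous diabetes code would persist once carried forward.

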of hypertension with index visit BP ≥140/90 mm Hg or no diagnosis of hypertension but two consecutive BP ≥140/90 mm Hg, or ACC/AHA 10-year CV risk ≥7.5% and LDL either untested or ≥70 mg/dL and not on a statin, (g) no hospice care or chemotherapy for cancer within previous 12 months, and (h) have at least one subsequent primary care visit after the index visit. The patient accrual period (for first index visits) will be 12 months, followed by a 26-month observation period. Thus, patients will have 26 to 38 monthsof follow up, with an expected median of 32 months follow up after the index visit. Pilot data indicate that non- pregnant eligible adults have a median of 6 primary care visits over a 24-month period, ensuring broad inclusion in the analysis. We conservatively estimate an average of 25 eligible patients per consented study PCP with few losses due to death (<1%) in the study period. Few patients switch primary care clinics in Essentia and we accurately match over 98% of patients to a regular PCP. Ultimately, after accounting for all eligibility criteria, we anticipate over 6,600 eligible patients for Aim 1 and Aim 2 analyses. For Aim 1 and Aim 2 analyses we will retrospectively collect CV clinical information and will ask for a waiver of patient consent. The IRB has waived consent in prior and existing evidence-based CDS studies. Patients specifically recruited for focus groups and surveys will be consented and receive

modest compensation for those activities.

Description of Usual Care (UC) and PrediabetesCDS Intervention Conditions.

[figure not shown]
UC Condition. UC clinics and their consented PCPs will have no access to the CDS intervention.

Prediabetes CDS System: The Prediabetes CDS intervention is rooted in a series of antecedent studies that have developed successful forms of CDS for diabetes. The process flow of the intervention is shown in Figure 2.Specific steps in implementation of the Prediabetes CDS intervention are described below.

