Step D: Presentation of Prioritized CV Treatment Options to PCPs and Patients. The CDS clinic workflow is illustrated in Figure 2. At a clinic visit, the following protocol is automatically implemented: (1) When the rooming nurse enters the patient BP in the EHR, biometric data is automatically transferred to a secure Web server. If the patient has prediabetes, is overweight or obese, and has atleast one other elevated CV risk factor, a "Best Practice Alert" (BPA) automatically displays; (2) based on the BPA, the nurse deploys the CDS with a single click on the visit navigator and, with an additional click, prints the patient and PCP interfaces; (3) if a patient's mental and physical status appears stable. the nurse hands the patient interface sheet(Figure 3) to the patient, saying, "The yellow marks show how you can reduce your danger of diabetes, stroke, or heart attack later in life. If you are ready to work on any of these things, please talk with your doctor during your visit today."

Figure 3. Patient Version of Clinical Decision Support System. Can you reduce your danger of heart attack and stroke? fes, you can! If you want to avoid a heart attack or stroke, talk to your doctor about what you can do about the hings with the most 🛕 signs. The things with the 🤣 are ok. 5/6/2011 04/23/2011 161/87 5/6/2011 Weight Aspirin Use Date 04/23/2011 11/01/2011 0 Talk to your doctor about anything with one or more A symbols. Take notes improve your heart health:

(4) If the PCP prefers, the printed PCP interface is placed in the basket outside the exam room for visit planning before entering the exam room. Otherwise, the PCP interface is displayed when the PCP opens the EHR during the visit. The printed PCP interface is a powerful visit-planning tool that most PCPs prefer to view before entering the exam room; (5) the PCP discusses patient questions or treatment preferences related to the prioritized CV risk reduction or diabetes prevention CDS recommendations; and (6)based on patient preferences, the PCP completes the Prediabetes Smartset (see below) or books a follow-upvisit.

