Step F: Iterative Use of the Prediabetes CDS over a Series of Visits. A key design feature of this intervention is its repeated use at all office visits of eligible patients during the intervention period. The CDS is automatically activated at any visit during the study period for eligible patients and provides updated treatment priorities and recommendations at each visit. Pilot data indicate that eligible patients average 4-6 primary care visits during a 24 month period, assuring that nearly all intervention patients have at least 3 exposures to the CDS. The CDS can also be manually activated by the PCP. In our previous study, almost 70% of eligible PCPs maintained use of the CDS system. With strong support from Essentia leaders and PCP leaders, we expect similar use rates.

Prediabetes patients converting to diabetes will continue to receive appropriate CV risk reduction prioritization and evidence-based glucose and aspirin treatment recommendations, thus facilitating timely treatment transition for newly diagnosed diabetes and reducing the lag time often reported between conversion to diabetes and being clinically diagnosed and treated.

Implementation of the Prediabetes CDS Intervention: Key implementation stages include: organizational engagement; adapting, piloting, and refining the Prediabetes CDS; and implementing the Prediabetes CDS group-randomized study. Key informant interviews, focus groups, surveys, usability testing, EMR data, and continuous quantitative and qualitative feedback between researchers and stakeholders will be used to monitor the implementation process and outcomes.

Organizational Engagement: As part of the initial engagement process, Essentia leaders and PCP leaders have already provided letters of support for the prediabetes CDS. Further engagement with Essentia leadership, informatics personnel, and key providers will occur through in-person meetings, conference calls, informational meetings, and identification of critical personnel to participate in the development, adaptation, and piloting processes of this study.

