webinars and email reminders with links to a short instructional video demonstrating rooming nurse and PCP roles in prediabetes CDS use. Training will be completed and the CDS fully implemented at all intervention clinics within 30 working days of clinic randomization. To ensure high intervention implementation fidelity, all intervention clinic staff will receive weekly email reports showing CDS rates of use among all eligible patients. The project manager will communicate (in-person, by e-mail, or by telephone) with each Intervention clinic's nurse managers each month throughout the full implementation period to assess continued use of the CDS and to gather feedback. Furthermore, the CDS provides an open-ended feedback mechanism for providersto give implementation researchers and staff timely feedback on issues, concerns, and proposed refinements about the CDS so it can be more effectively and efficiently implemented and used at the intervention clinic sites.

Ongoing communication and feedback with stakeholders throughout the engagement, adaptation, pilot testing, and implementation phases will allow us to assess various components of the RE-AIM and CFIR frameworks to best determine mediators of CDS implementation, use, clinical outcomes, and future implementation and dissemination throughout Essentia primary care clinics and other health systems.

Definition and Measurement of Variables: We will use a mixed-methods approach to examine the facilitators and barriers for (a) successfully achieving and maintaining CV risk factor control among prediabetespatients at high CV risk (Specific Aim 1) and for (b) sustainable implementation in Essentia primary care clinics(Specific Aims 2 & 3). Appendix A contains the protocol for measuring the study variables.

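### Criterion (h) selects patients on a visit after index that the CDS could influence; this may bias the Aim 2 cost contrast, probably by a small amount, and is avoidable

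*Combined protocol and SAP*

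**What the plan says.** Under Group-Randomized Study Eligibility Criteria, the patient criteria open with "To be considered for inclusion in primary or secondary analyses" and state that patients must "meet all the following eligibility criteria at the time of their indexvisit". Criterion (h), the last in the list, is that they "have at least one subsequent primary care visit after the index visit". It has no time window. Aims 1 and 2 share the resulting set: "after accounting for all eligibility criteria, we anticipate over 6,600 eligible patients for Aim 1 and Aim 2 analyses". The number removed by (h) is not given.

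On exposure, the section on implementing the randomized study has "the CDS fully implemented at all intervention clinics within 30 working days of clinic randomization", and Step F says "The CDS is automatically activated at any visit during the study period for eligible patients". In Step D, item (6), acting on patient preferences, "the PCP completes the Prediabetes Smartset (see below) or books a follow-upvisit". Step E lists patient follow-up among the things the Smartset groups together. UC clinics have no access to the CDS.

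Aim 2 costs are taken from Essentia billing and encounter data up to 24 months after index. The Aim 2 model is a GEE, typically gamma with log link. Neither the Aim 2 analytic approach nor the Missing data paragraph mentions patients removed by (h).

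**The concern.** Whether (h) is met cannot be known at index. It is settled after clinic randomisation and, in a CDS clinic, possibly after first exposure to the intervention. The CDS arm alone has a workflow and an order set that prompt follow-up, so treatment has a route to influence who enters the analysis. The covariates section itself lists the number of primary care encounters as a possible dependent outcome, moderator or mediator.

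Aim 2 is where this matters. Costs can be measured from billing data whether or not the patient returns, so (h) is not needed there. Patients who never return are plausibly low-cost. If the CDS brings back marginal patients whom UC does not, (h) removes more low-cost patients from UC than from CDS. The UC mean is then raised relative to the CDS mean, and the added cost of the CDS is understated.

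**Working it through.** The plan gives no figure for the loss under (h), so there is nothing to reproduce. Its power calculation concerns the H1 slope and does not bear on this point.

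**Inputs from the plan.** Pilot visits are given as a median of 6 per 24 months (Study Participants) and as an average of 4 to 6 per 24 months (Step F). Follow-up is 26 to 38 months, with an expected median of 32. Mean visits over 32 months are therefore μ = 4 × 32/24 = 5.33 to 6 × 32/24 = 8.

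**Assumptions, not in the plan.** Negative binomial dispersion k = 1 to 4; 20% more visits in CDS clinics; non-returners cost a fraction f = 0 to 0.2 of a returner in the same arm.

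**Step 1: share without a return visit.** P0 = (k/(k+μ))^k for the negative binomial and exp(−μ) for Poisson. CDS uses 1.2μ.

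| Visits per 24 months | Model | UC | CDS | Difference (points) |
|---|---|---|---|---|
| 4 | NB, k = 1 | 15.8% | 13.5% | 2.3 |
| 4 | NB, k = 4 | 3.4% | 2.2% | 1.2 |
| 6 | NB, k = 1 | 11.1% | 9.4% | 1.7 |
| 6 | NB, k = 4 | 1.2% | 0.7% | 0.5 |
| 4 | Poisson | 0.48% | 0.17% | 0.3 |
| 6 | Poisson | 0.03% | 0.01% | 0.03 |

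At the shortest follow-up, 26 months, the Poisson share is 0.15% at 6 visits per 24 months and 1.3% at 4.

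**Step 2: effect on the cost ratio.** If returners in an arm have mean cost R, all index patients in that arm have mean R[(1−p) + pf], where p is the non-return share. The CDS/UC ratio in all index patients is therefore the (h)-restricted ratio multiplied by

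[(1−pC) + pC·f] / [(1−pU) + pU·f].

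- Largest case (4 visits, k = 1, f = 0): (1−0.1351)/(1−0.1579) = 0.8649/0.8421 = 1.027, understated by 2.7%.
- Smallest negative binomial case (6 visits, k = 4, f = 0.2): (1−0.8×0.00748)/(1−0.8×0.01235) = 0.99402/0.99012 = 1.004, understated by 0.4%.
- Poisson: 0.02% to 0.3%.
- Equal non-return in both arms: the factor is 1 and there is no bias.

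**Step 3: cross-check with a different model.** Suppose there is no cost effect in patients who would return in either arm, non-returners cost 10% of a returner, and patients who return only because of the CDS cost 50%. With assumed non-return of 5% in UC and 3% in CDS, the restricted ratio is (0.95 + 0.02×0.5)/0.97 = 0.990. In all index patients it is (0.96 + 0.03×0.1)/(0.95 + 0.05×0.1) = 0.963/0.955 = 1.008. The restricted ratio is 1.9% too low. With 2% and 1% it is 0.9% too low, and with 5% in both arms the two ratios agree. The direction is the same.

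**The case against.** The strongest reply is that a pathway is not an effect. A reader might infer that the analysis set is in fact selected differently by arm and that the Aim 2 result is biased. The documents do not show that: they give no return rate by arm. Booking follow-up is a clinician's action, offered as an alternative to the Smartset, and UC clinicians can book visits too. This stands.

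The dispersion is also an assumption, and its upper end fits the plan poorly. With k = 1 and a mean of 4 visits the median would be 3, against the stated 6. An average at or below the median does not suggest strong right skew. This counsels against relying on the top of the range. It is not full reassurance, because the pilot figures describe eligible adults and may already be conditioned on returning.

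A larger gap, such as 10% against 6% without a return visit, would give up to 4.4% (0.94/0.90 = 1.044 at f = 0). But that is a 4-point difference, and 20% more visits yields at most 2.3 points in Step 1, so the figure is not supported.

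Third, low cost in a non-returner may be unobserved cost. The Aim 2 cost section concedes that Essentia billing can miss care elsewhere. Including patients who left the system could therefore overstate the added cost of the CDS. This is a real caveat on the remedy and a reason to report both sets.

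Finally, the assumed direction works against H4 as worded, which predicts lower costs in UC, so it would not create false support for that hypothesis. That is correct, but the estimate of added cost would still be too low.

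**Conclusion.** The point holds in limited form. Criterion (h) is an inclusion rule decided after randomisation and possibly after exposure, listed as if met at index. It is applied to Aim 2, where it is not needed, with no arm-level count or sensitivity analysis planned. It could bias the H4 contrast. The size is about 0.4 to 2.7% of the cost ratio under the stated assumptions on dispersion, visit increase and non-returner cost, negligible under Poisson visits, and zero if return rates are equal.

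Three further inferences are not supported:

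- **That Aim 1 is compromised.** An index-only patient carries no slope information and the model conditions on the index value, so H1 and H2 are hardly affected by dropping (h).
- **That non-returners were unexposed.** The CDS can fire at the index visit.
- **That (h) explains the fall from over 11,000 patients in Specific Aim 1 to over 6,600.** The plan does not attribute that difference to (h).

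Confidence is high on the design point and moderate on the size.

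**What to change.** 1. Define the Aim 2 analysis set as all patients meeting (a) to (g) at index. Leave the Aim 1 set as it is.
2. Correct the eligibility wording so that (h) is described as a condition assessed after index.
3. Report the number and proportion without a return visit in each arm.
4. Keep the (h)-restricted set as an Aim 2 sensitivity analysis and present the two results together.

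The cost is an edit to the analysis plan and a wider extract of data that are collected retrospectively under the requested consent waiver. There are two downsides. Some patients may have zero cost, so the model must keep zeros, through a suitable GEE mean-variance form or a two-part model; if index-visit costs are counted, zeros may be few. Some non-returners may have left the system, so their low Essentia cost may be unobserved. State that limitation when comparing the two analyses. The document already records lack of efficacy, so if Aim 2 has been run, label the added analysis as post hoc.
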